8.2.4.2. Scanning Procedures

For women of child-bearing potential, a urine pregnancy test will be performed on the same day, and prior to, the PET scan at Imperial College in London. If the result of this test is positive, the PET procedure will not be performed and the patient will be monitored as outlined in Section 7.2.

Specific activity, chemical purity, and radiochemical purity of ^{11}C -PBR28 will be determined by radio high performance liquid chromatography (HPLC) coupled with a gamma detector. Specific activity will be determined by counting an aliquot in a dose calibrator and determining the mass by HPLC against a calibration curve of the cold standard. Identity will be confirmed by co-injecting the standard.

Approximately 400 MBq of ^{11}C -PBR28 as intravenous bolus will be injected, and an approximately 90 minutes emission PET-CT scan will be acquired on a Siemens HiRez 6 PET/CTI scanner (Siemens Healthcare, Erlanger, Germany). A low dose CT scan of the head will be performed immediately before each PET study for subsequent attenuation and scatter correction of PET signal. Imaging data will be reconstructed with filter backprojection (direct inversion Fourier transform) with a 128 matrix, a zoom of 2.6, a transaxial Gaussian filter of 5 mm, scatter correction and attenuation correction. All subjects will have a volumetric T1-weighted MR sequence for co-registration purpose with PET images.

Patients will be advised that they should not participate in further research studies involving ionizing radiation for a year following the last performed scan.

8.3. Pharmacogenomic Variables

It is recognized that genomic variation within the population can be an important contributory factor to inter-individual differences in drug response. Pharmacogenomic (PGx) studies investigate the association between genetic sequence polymorphisms and/or gene expression signatures and clinical response to a certain therapeutic intervention. It may help explaining inter-individual variability and subsequently identify population subgroups that respond differently to the drug. Furthermore, regulatory guidance and white papers indicate that PGx analyses employing DNA collected from all study participants may support investigation of unexpected adverse events.

In order to allow any subsequent analyses, appropriate samples will be requested from all patients in the study. PGx assessment will include CAG repeats analysis in huntingtin gene and might also include other DNA variations and RNA expression patterns potentially associated with clinical treatment responses to laquinimod (e.g. clinical effect, pharmacokinetics, tolerability, and safety features or disease susceptibility and severity features). The final list of genes that might be investigated will be selected in a later stage before the analysis so as to allow updating with new scientific information. Genomic analysis could also include a sequencing of the whole genome if required.

PGx assessment will be performed if variability in response measurements is observed and attributable to genomic parameters. Samples might be used for investigations related to CNS disorders diseases and/or response to laquinimod or related investigational drugs.

8.3.1. Methods and Timing of Pharmacogenomic Blood Sampling

PGx assessment will be performed using blood samples.

- Blood samples for DNA extraction will be collected at screening (or if not possible, at the next possible visit) in **two** 5.0 mL K3 EDTA Vacutainer plastic tubes (or equivalent).
- Blood samples for gene expression analysis (RNA extraction) will be collected at baseline, Month 6 and Month 12 from all subjects in PAXgene RNA 10 mL tubes (or equivalent).

PGx samples will be stored for a period of up to 15 years from patient last visit in the main study and then destroyed.

8.3.2. Shipment of Samples

PGx samples will be stored at -70°C (if -70°C storage is not possible at the site, store at -20°C) and sent to the central laboratory on dry ice. Following DNA and RNA extractions, the samples will be stored at -70°C and labeled with a new code, so genomic data will not be recorded with subject number or initials. Data will be kept confidential and stored separately.

The PGx sample analyses will be performed if and when required. Since new PGx techniques continue to be developed, we cannot anticipate the method and laboratory that will be recommended for the DNA/RNA analysis.

9. STATISTICS

9.1. Study Design and Randomization

This is a double-blind, randomized, placebo-controlled, parallel-group study to evaluate the efficacy and safety of laquinimod (0.5 mg and 1.0 mg qd) treatment in patients with HD. Prior to 10 January 2016, eligible patients were randomly assigned to receive treatment with laquinimod at a dosage of 0.5 mg, 1.0 mg, or 1.5 mg/day or a matching placebo in a 1:1:1:1 ratio. Randomization will be as described in Section 3.3.

As of 10 January 2016, following a decision to discontinue treatment of the laquinimod 1.5 mg dose arm, future eligible patients will be randomized in a 1:1:1 ratio to receive laquinimod 0.5 mg/day or 1.0 mg/day or matching placebo for 52 weeks.

No change was performed to the original randomization list except that the patient numbers assigned to laquinimod 1.5 mg/day were removed from the list by the IRT vendor. Patients and investigators will remain blinded to treatment assignment during the study.

All patients who discontinued the 1.5 mg/day dose have been unblinded. No attempts will be made to re-randomize patients whose 1.5 mg treatment was stopped to a lower dose of laquinimod. The remaining ongoing patients retained their originally randomized treatment assignments.

9.2. Sample Size and Power Considerations

The study aims to detect potential beneficial effects in deteriorating clinical signs and symptoms. Based on previous studies in patients with HD, the UHDRS-TMS has been shown to be one of the more sensitive clinical measures to detect decline in symptoms of HD. It is estimated that approximately 100 patients per arm will enable a power of 80% to detect a beneficial effect compared to placebo, of 2.5 points or more in the change from baseline in UHDRS-TMS of an active laquinimod arm, assuming SD of 6.2 and type I error of 5%.

As the intention is to investigate laquinimod as a treatment with the potential to slow disease progression and prohibit neuronal death in the CNS, the study should also be sized to be able to detect changes in brain atrophy rate after treatment with laquinimod. One of the most sensitive measures to detect brain atrophy over time in patients with HD is change in the caudate volume.

It is estimated that approximately 100 patients per arm will enable a power of 80% to detect a beneficial effect of 0.95 (30% of the estimated decline in placebo) or more in the percent change from baseline in caudate brain atrophy of an active laquinimod arm compared to placebo, assuming SD of 2.36 and type I error of 5%.

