Pharmacogenomic (PGx) assessment will include DNA variations and RNA, gene expression pattern potentially associated with clinical treatment responses to laquinimod (e.g. clinical effect, Q-Motor, pharmacokinetics, tolerability, and safety features or disease susceptibility and severity features). Samples for DNA analysis will be collected at screening (or if not possible, at the next possible visit). Samples for RNA analysis will be collected at baseline, Month 6 and 12.

Other Ancillary Studies:

- Microglial activation state will be investigated in selected patients (N=aiming at 10 per treatment arm). Positron emission tomography (PET) scans and imaging analysis of microglial activation marker translocator protein (TSPO) will be performed at baseline and Month 12.
- Change in putaminal and frontal white matter markers of neuronal integrity (N-acetyl-aspartate (NAA)) and astrocytosis (myo-inositol) will be investigated at selected sites using magnetic resonance spectroscopy (MRS) (N=aiming at 20 per treatment arm) at baseline and Month 12.
- Monocyte gene expression and/or protein profile in response to treatment with laquinimod will be analyzed at selected sites and patients (N=aiming at 25 per treatment arm). Monocytes will be separated from isolated peripheral blood mononuclear cells (PBMC) and be analyzed for gene expression and/or protein profile at baseline and Month 12.
- Peripheral cytokine and proteomic analysis in response to treatment with laquinimod will be investigated in a subgroup of patients at selected sites at baseline and Months 6 and 12.

Statistical Considerations:

Sample Size

The study aims to detect potential beneficial effects in deteriorating clinical signs and symptoms. Based on previous studies in patients with HD, the UHDRS-TMS has been shown to be one of the more sensitive clinical measures to detect decline in symptoms of HD. It is estimated that approximately 100 patients per arm will enable a power of 80% to detect a beneficial effect of 2.5 points or more in the change from baseline in UHDRS-TMS of an active laquinimod arm compared to placebo, assuming standard deviation (SD) of 6.2 and type I error of 5%.

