As the intention is to investigate laquinimod as a treatment with the potential to slow disease progression and prohibit neuronal death in the CNS, the study should also be sized to be able to detect changes in brain atrophy rate after treatment with laquinimod. One of the most sensitive measures to detect brain atrophy over time in patients with HD is change in the caudate volume. It is estimated that approximately 100 patients per arm will also enable a power of 80% to detect a beneficial effect of 0.95 (30% of the estimated decline in placebo) or more in the percent change from baseline in caudate brain atrophy of an active laquinimod arm compared to placebo, assuming SD of 2.36 and type I error of 5%.

Statistical Analyses

Due to the decision from 10 January 2016 to discontinue treatment of the laquinimod 1.5 mg dose arm, and the low number of enrolled patients compared to the target at this time, data from the laquinimod 1.5 mg treatment arm will be presented descriptively only, and will not be included in any inferential analyses for efficacy or safety.

Control of Type I Error Rate

The Hochberg's Step-Up method for multiple comparisons between treatment arms in combination with the hierarchical method between the primary efficacy endpoint and the secondary efficacy endpoints, will be used to maintain the experiment wise type I error of 5% level.

Primary Efficacy Endpoint Analysis

The change from baseline in UHDRS-TMS will be analyzed using a Repeated Measures model (SAS® MIXED procedure with REPEATED sub-command). The model will include the following fixed effects: categorical week in trial by treatment interaction, center, and UHDRS-TMS at baseline. The unstructured covariance matrix for repeated observations within patients will be used. In case that the model will not converge, the Maximum-Likelihood (ML) estimation method will be used instead of the default Restricted ML (REML). If the model still does not converge then a simpler covariance structures with less parameters will be used, according to the following order: Heterogeneous Autoregressive(1) [ARH(1)], Heterogeneous Compound Symmetry (CSH), Autoregressive(1) [AR(1)], and Compound Symmetry (CS). The estimated means at the Month 12 visit will be compared between the active treatment arms and the placebo arm.

The Hochberg's Step-Up method for multiple comparisons between treatment arms will be used to control inflation in type I error rate.

Secondary Efficacy Endpoints Analyses

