9.6.2.2. Secondary Efficacy Endpoints Analyses

According to the hierarchical method to control inflation in type I error rate for multiple endpoints, any statistically significant dose that will be observed in the primary analysis will continue to be tested for the secondary endpoints at an alpha level of 5%, according to the secondary endpoints order.

The secondary efficacy endpoints: change from baseline in HD-CAB total score and change from baseline in UHDRS- TFC, will be analyzed in the same way as the primary efficacy endpoint except that the efficacy endpoint evaluation at baseline will be included in the model instead of baseline UHDRS-TMS.

The CIBIC-Plus will be analyzed in the same way as the primary efficacy endpoint except that the baseline CIBIS (Clinician's Interview-Based Impression of Severity) will be included in the model as the efficacy measure at baseline.

The percent change from baseline to Month 12/Early Termination in caudate volume will be analyzed using an Analysis Of Covariance (ANCOVA) model (SAS® MIXED procedure). The model will include the following fixed effects: treatment, center, and caudate volume at baseline.

The estimated means at the Month 12 visit will be compared between the active treatment arms and the placebo arm. Early terminated patient observation will have their Last Observation Carried Forward (LOCF).

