9.7. Multiple Comparisons and Multiplicity

The Hochberg's Step-Up method for multiple comparisons between treatment arms in combination with the hierarchical method between the primary efficacy endpoint and the secondary efficacy endpoints, will be used to maintain the experiment wise type I error of 5% level. First, the Hochberg method will be applied for the comparisons of the 2 active doses to placebo in the primary endpoint analysis. Then, using the hierarchical method, any statistically significant dose will continue to be tested for the secondary endpoints at an alpha level of 5% and according to the order of the secondary endpoints.

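### The stated 80% power for TMS and caudate is that of one unadjusted, ungated 5% test, not of the Hochberg procedure and TMS gate the protocol specifies

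*Protocol*

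**What the plan says.** Section 9.2 gives two sizing statements. For the primary endpoint: "approximately 100 patients per arm will enable a power of 80% to detect a beneficial effect compared to placebo, of 2.5 points or more", with an SD of 6.2. For caudate volume: "approximately 100 patients per arm will enable a power of 80% to detect a beneficial effect of 0.95" percentage points, with an SD of 2.36. Each is stated at a type I error of 5%. The second is not offered as a by-product, because the section says that "the study should also be sized to be able to detect changes in brain atrophy rate". The synopsis repeats both claims ("approximately 100 patients per arm will enable a power of 80% to detect a beneficial effect of 2.5 points or more" and "approximately 100 patients per arm will also enable a power of 80% to detect a beneficial effect of 0.95").

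The testing procedure is in 9.6.2 and 9.7. Section 9.7 says: "First, the Hochberg method will be applied for the comparisons of the 2 active doses to placebo in the primary endpoint analysis". For what follows, 9.6.2.2 says that "any statistically significant dose that will be observed in the primary analysis will continue to be tested for the secondary endpoints", each at 5% and in the listed order. Caudate is first in that order (9.6.1.2). The whole scheme "will be used to maintain the experiment wise type I error of 5% level".

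**The concern.** Section 9.2 mentions neither the Hochberg step nor the gate. It gives a 5% type I error without saying that this is per comparison, while 9.7 attaches the same 5% to the experiment-wise error. A reader can therefore take 80% as the power of the planned tests.

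The caudate figure matters most. Under the hierarchy, a caudate claim for a dose needs two successes for that dose, first on TMS and then on caudate, so its probability cannot exceed that dose's TMS power. If 80% is read as the chance of a caudate claim, a missing claim will look like stronger evidence against an effect on atrophy than it is, because failure at the TMS gate may explain it.

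**Working it through.** **Inputs.** From 9.2: n = 100 per arm; TMS effect 2.5, SD 6.2; caudate effect 0.95, SD 2.36; alpha 5%. Sidedness is not stated and is taken as two-sided. From 9.1: equal allocation with one shared placebo arm, so the two dose-versus-placebo statistics correlate 0.5. From 9.6.2 and 9.7: Hochberg over two doses on TMS, then caudate at 5% for a dose that passed. Assumed here: 100 complete patients per arm (9.2 states no dropout allowance) and a within-patient TMS–caudate correlation between 0 and 0.5.

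**Step 1: reproduce the 80%.** The noncentrality is effect / (SD × √(2/n)).

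- TMS: 2.5 / (6.2 × 0.1414) = 2.851
- Caudate: 0.95 / (2.36 × 0.1414) = 2.846

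Against the two-sided 5% critical value, the noncentral t gives 81.0% and 80.9%, and 80% is reached at 98 per arm for both endpoints. By normal approximation, Φ(2.851 − 1.960) = 81.4% and Φ(2.846 − 1.960) = 81.2%. At two-sided 2.5% the t-based power is 72.3% and 72.1%. For TMS, a one-sided 5% test gives 88.6% (normal approximation). Only the unadjusted, ungated two-sided 5% test matches 80% at about 100 per arm.

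**Step 2: apply the plan's procedure.** Hochberg rejects for both doses if both p-values are below 0.05; otherwise it rejects only for a dose with p below 0.025. Three arms with a shared placebo were simulated (normal approximation, 2 million trials per cell). The stated SDs were taken as residual SDs. Caudate entries are for correlations of 0 / 0.3 / 0.5.

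| Scenario | TMS, full-effect dose | TMS, at least one dose | Caudate claim, full-effect dose | Caudate claim, at least one dose |
|---|---|---|---|---|
| One dose works, other inert | 73.2% | 73.2% | 59.5 / 62.4 / 64.5% | same |
| Other dose has half the effect | 74.1% | 74.9% | 60.2 / 63.1 / 65.3% | 60.9 / 63.9 / 66.2% |
| Both work fully | 79.0% | 87.5% | 64.2 / 66.8 / 68.8% | 78.7 / 80.4 / 81.8% |

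A hand check at correlation 0: the gated power is TMS power times caudate power, 0.732 × 0.812 = 0.594 with one effective dose and 0.790 × 0.812 = 0.641 per dose with two. Both agree with the simulation.

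Once the gate is passed, the caudate test itself has full power. With one effective dose, 59.5/73.2 = 81% at correlation 0 and 64.5/73.2 = 88% at 0.5. The loss comes from reaching the test.

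**Step 3: vary the assumptions.**

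- *Correlation 0.8:* the caudate claim is 69% with one effective dose and 73% per dose with both (85% for at least one).
- *SDs are raw, and baseline and centre explain an assumed 15% of variance on both endpoints* (SDs × √0.85): TMS becomes 80.6% with one effective dose and 85.5% per dose with both (92.2% for at least one). The caudate claim, over correlations of 0 to 0.5, becomes 70.1–73.8% with one dose and 74.4–77.6% per dose with both (86.7–88.5% for at least one).

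**The case against.** Section 9.2 speaks of a single active arm against placebo, which reads naturally as per-comparison power, and on that reading nothing in it is false. The secondary tests do run at 5%, so the caudate figure describes that test correctly once it is reached. If both doses work, TMS power is 79% per dose and 87% for at least one, which rounding of an approximate 80% would cover. The 73% needs the other dose to be inert or clearly weaker, and Section 1.5 regards 0.5 mg as probably effective. The SD basis is unstated, and modest covariate adjustment removes the TMS shortfall. The correlation is assumed. Power under multiplicity scenarios could also be left to a statistical analysis plan.

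Much of this stands, and it limits the size of the point. The TMS gap is slight if both doses work equally, and the exact caudate figures depend on inputs the protocol does not supply. Three things remain. First, the protocol itself fixes both the power statement and the procedure, so the mismatch lies within this document. Second, Section 1.5 does not support assuming equal effects: it describes 0.5 mg as thought to be the lowest effective dose, and reports differing results for 0.5 and 1.0 mg in Crohn's disease and lupus nephritis. Third, per-dose power for a caudate claim stays below 80% in every case computed, although 9.2 names atrophy as a basis for the sample size.

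**Conclusion.** The point holds. The 80% figures are correct for one unadjusted, ungated comparison, but they are not labelled so and are not the power of the procedure in 9.6.2 and 9.7.

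At the stated SDs and correlations of 0 to 0.5, the chance of a caudate claim for a fully effective dose is 11 to 20 points below 80%. For at least one dose it is near 80% only if both doses work fully; otherwise it is about 60–66%. The TMS shortfall is about 7 points with one effective dose and about 1 point per dose with two.

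The direction is secure. The exact caudate values rest on the assumed correlation, on complete data and on the stated SDs being residual SDs. Type I error control is unaffected. This is a minor to moderate misstatement of what the design delivers, not a fault in the analysis.

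**What to change.** In 9.2 and the synopsis:

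1. Label each 80% as per-comparison power before the Hochberg adjustment and the TMS gate of 9.7.
2. Add TMS power under Hochberg: about 73% with one effective dose, 74% for the full-effect dose if the other has half the effect, and 79% per dose (87% for at least one) if both work.
3. Add the power for a caudate claim through the gate: about 60–65% with one effective dose, and 64–69% per dose (79–82% for at least one) if both work.
4. State with these figures the dose scenario, the assumed correlation and whether 6.2 and 2.36 are raw or residual SDs. If they are raw, use figures based on the adjusted SDs.

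The cost is a few sentences and less favourable per-dose figures. Sample size, analysis and conduct do not change.

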9.3. Analysis Sets/Populations

Due to the decision from 10 January 2016 to discontinue treatment of the laquinimod 1.5 mg dose arm, and the low number of enrolled patients compared to the target at this time, data from the laquinimod 1.5 mg dose arm will be presented descriptively only and will not be included in any inferential analyses for efficacy or safety.

9.3.1. Intent-to-Treat Population

The intent-to-treat (ITT) population will include all randomized patients. In this population, treatment will be assigned based on the treatment to which patients were randomized, regardless of which treatment they actually received.

9.3.2. Safety Population

The safety population will include all randomized patients who receive at least 1 dose of study drug. In this population, treatment will be assigned based upon the treatment patients actually receive, regardless of the treatment to which they were randomized.

9.3.3. Full Analysis Set (FAS)

The full analysis set (FAS) will include all patients in the ITT population who receive at least 1 dose of study drug and have at least 1 post-baseline efficacy assessment.

9.4. Data Handling Conventions

For all variables, only the observed data from the patients will be used in the by visit summary.

For efficacy endpoints that are measured at baseline and at month 12 only, the Last Observation Carried Forward (LOCF) method will be applied for early terminated patient observation.

Detailed data imputation rule will be specified in the statistical analysis plan.

9.5. Study Population

The ITT population will be used for all study population summaries unless otherwise noted. Summaries will be presented by treatment group and for all patients.

The Safety population will be used for safety variables.

The FAS will be used for efficacy variables.

9.5.1. Patient Disposition

Data from patients screened, patients screened but not treated, patients in the safety population and FAS, patients who complete the study, and patients who withdraw from the study will be summarized using descriptive statistics. Data from patients who withdraw from the study will also be summarized by reason for withdrawal using descriptive statistics.

